8.4 Data Analysis

Descriptive statistics will be provided for the key endpoints, including measures of central tendency (mean or median, as appropriate), measures of variation (standard deviations, coefficients of variation) and 95% confidence intervals and interquartile ranges, as appropriate. Specifically, these measures will be calculated for:

- Changes in wound size
- Average percent periwound global score reduction
- Subject's pain rating during dressing changes
- Dressing shrinkage determined upon removal of dressings
- Proportion of subjects who develop an infection

The key assessment for differences in dressing performance will be based on the comparison of mean reduction in wound size for each dressing type. The specific details of the statistical testing will be provided in a forthcoming SAP. Comparisons of reduction in PUSAS score, subject pain ratings, and dressing shrinkage will also be made between the two dressing types, with specific details described in the SAP.

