2.3. Risk/Benefit Profile

2.3.1. Potential Study Risks

Subjects may experience an allergic reaction to MPS-Ag dressing, CMC-Ag dressing, compression bandage, wound cleanser, or skin protectant. Therefore, to mitigate this risk, subjects will be screened for known sensitivity to MPS-Ag, CMC-Ag, or compression bandage dressings, and other commonly used dressings, as well as other clinical products used in this study. Additionally, subjects will be under the care of a physician, who will be able to appropriately address any potential reaction from the dressings.

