6.3 Dressing change visits - weekly and unscheduled

Subjects will have dressings removed at least once weekly (except on the initial visit) followed by application of new dressings. This will continue for eight weeks, from the initial visit, unless participation of the subject is terminated earlier as in section 4.2. The dressing change form will be completed at the initial visit and other subsequent dressing change visits. Additional information such as current analgesic, any new medication, irritation around the wound bed, and any abnormality in the wound status will be captured. If the clinician feels that the peri-wound tissue requires protection, a skin protectant may be applied by the clinician or the clinical staff, per the facility's standard of care and clinician's discretion, and will be recorded. The following information will also be recorded on the dressing change form:

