7 ADVERSE EVENTS

7.1 Definition of Adverse Event

In this study, an adverse event (AE) is any untoward medical occurrence related to the wound or treatment of the wound, including infection or a significant increase in pain during dressing changes.

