7.5 Expectedness

The site PI will be responsible for determining whether an AE or SAE is expected or unexpected. An AE will be considered unexpected if the nature, severity, or frequency of the event is not consistent with the risk information previously described for the study intervention.

Expected AEs include a reaction or irritation at the wound site following application of the wound device or infection.

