7.6 Adverse Event Reporting

The AEs will be recorded on the AE form by the study staff and reviewed by the site PI. Changes in the severity of an AE will be documented to allow an assessment of the duration of the event at each level of severity. Changes in severity will necessitate a new CRF to document the new level of severity. AEs characterized as intermittent require documentation of onset and duration of each episode.

Non-serious AEs are to be reported to the study sponsor on a monthly basis for review or as agreed upon with the study sponsor and reported to the IRB per IRB reporting requirements.

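### Section 8.4 specifies no by-dressing summary of adverse events or wound-site reactions apart from infection, and section 8.3 restricts any safety proportion to subjects with a valid final wound measurement

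*Combined protocol and SAP*

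**What the plan says.** **Harms foreseen.** Section 2.3.1 states: "Subjects may experience an allergic reaction to MPS-Ag dressing, CMC-Ag dressing, compression bandage, wound cleanser, or skin protectant". It names allergic reaction only. Section 7.5 adds: "Expected AEs include a reaction or irritation at the wound site following application of the wound device or infection". Section 7.1 defines an adverse event as an untoward occurrence related to the wound or its treatment, "including infection or a significant increase in pain during dressing changes".

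**Harms recorded.** Section 6.3 says of visits to change the dressing: "Additional information such as current analgesic, any new medication, irritation around the wound bed, and any abnormality in the wound status will be captured". It also says: "The dressing change form will be completed at the initial visit and other subsequent dressing change visits". Sections 7.3 to 7.5 have events graded and assessed for relatedness and expectedness. Section 7.6 adds: "The AEs will be recorded on the AE form by the study staff and reviewed by the site PI".

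**Harms analysed.** Section 8.4 lists five quantities: wound size change, periwound score reduction, pain rating, dressing shrinkage, and "Proportion of subjects who develop an infection". Besides wound size, the between-dressing comparisons are given as: "Comparisons of reduction in PUSAS score, subject pain ratings, and dressing shrinkage will also be made between the two dressing types". Test details are left to a SAP still to come.

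**Who is analysed.** Section 8.3 applies one population to every analysis: subjects with valid wound size at both the initial and the final visit. Section 6.3.2 ends participation on culture-confirmed infection or antibiotic treatment of the study wound. Section 4.2 replaces subjects who withdraw.

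**The concern.** Section 7.5 pairs reaction or irritation with infection, but only infection reaches section 8.4. The synopsis asks which dressing better manages the wound and the surrounding skin. The trial is open-label, and the sponsor makes one of the two dressings. Followed as written, the protocol could report a wound size advantage without specifying how many subjects on each dressing had a reaction, how severe it was, or whether it was judged related.

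The population rule matters more than the missing table. A routine adverse event table could be added later, but under 8.3 it would still leave out subjects whose harm ended their participation before a valid final measurement. The infection proportion that is already listed has the same weakness.

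**Working it through.** **1. From harm to analysis**

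| Harm | Foreseen | Recorded | In 8.4 list | Named between-dressing comparison |
|---|---|---|---|---|
| Reaction or irritation at wound site | 7.5 (allergic reaction also in 2.3.1) | Irritation in 6.3; AE form in 7.6 | No | No |
| Infection | 7.5 | 6.3.2; AE form | Proportion | No |
| Pain at dressing change | 7.1, if significantly increased | 6.3.1 | Rating | Yes |
| Periwound skin (PUSAS) | Secondary objective | 6.2.3, 6.4 | Average percent reduction | Yes |
| Any AE, SAE, worst grade | 7.1 to 7.5 | AE and SAE forms | No | No |

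The Schedule of Activities has PUSAS at the initial, weekly and final visits but not at unscheduled dressing changes. An average percent reduction also lets a few subjects who worsen be offset by others who improve.

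**2. The plan's own sample size (8.1)**

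Inputs: difference 40 − 33 = 7 points, SD 10, two-sided alpha 0.05, 1:1 allocation. Exact t-test power is 0.7997 at 33 per arm and 0.8116 at 34 per arm, so 34 per arm (68 in total) is reproduced. The target of 80 equals 68/(1 − 0.15), which allows 80 − 68 = 12 subjects with incomplete data.

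**3. What the 8.3 rule can hide**

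Assume 40 treated per arm, the 12 losses split 6 and 6, and 34 evaluable per arm. The documents do not say why subjects will be lost, so the events among the 6 non-evaluable subjects in an arm can range from 0 to 6.

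| Events among 34 evaluable | Reported | Possible among 40 treated |
|---|---|---|
| 0 | 0% | 0/40 to 6/40 = 0% to 15.0% |
| 2 | 2/34 = 5.9% | 2/40 to 8/40 = 5.0% to 20.0% |

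Replacement under 4.2 could raise the number treated further. The protocol does not say whether the 80 includes replacements.

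**4. What a by-dressing table could show**

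No reaction rate is given, so the rates here are assumptions.

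- Zero events, exact two-sided 95% upper limit, 1 − 0.025^(1/n): 10.3% at n = 34 and 8.8% at n = 40.
- Half-width of the 95% CI for a difference at a common rate of 10%, 1.96 × √(2 × 0.1 × 0.9/n): 14.3 points at n = 34 and 13.1 points at n = 40.
- Fisher exact power, 5% v 20%: 0.31 at 34 per arm and 0.41 at 40.
- Fisher exact power, 5% v 30%: 0.72 at 34 per arm and 0.82 at 40.

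In row one of the table in step 3, the possible 15.0% lies above the 10.3% limit that the evaluable set would report.

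**The case against.** **Section 8.4 may not be exhaustive.** Its list is introduced as covering key endpoints, a SAP is to follow, and 4.2 promises a clinical study report. Adverse event tables could sit in either. This stands to the extent that silence does not show adverse events will go unreported by arm; the finding is only that the protocol specifies no such summary. However, the list already includes infection, which is not a section 3 endpoint, and 8.4 defers the testing and the named comparisons to the SAP, not safety reporting. A later table would also still fall under 8.3.

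**Harm is partly compared already.** A reader might infer that the plan never compares reactions, or that infection is its only safety item. The documents support neither. PUSAS measures periwound skin and is compared between dressings, so irritation present at a weekly visit can affect it. Pain ratings are compared too, and a significant increase in pain is an adverse event. What is missing is a count of subjects affected.

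**Allergic reaction and irritation are different things.** Section 2.3.1 names only the former, and 6.3 names only irritation around the wound bed. It would be wrong to say that allergic reaction is a named item at every dressing change, or that reaction is the only harm foreseen. What subjects were told cannot be checked.

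**Infected subjects may still be evaluable.** A reader might infer that 8.3 removes every infected subject, because 6.4 places the final visit at eight weeks or healing. The protocol does not say whether a measurement at termination counts as final, so the loss is certain only for subjects without a valid final measurement.

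**Conclusion.** The point holds as a gap in the protocol as written. No by-dressing summary of adverse events or of wound-site reaction or irritation is specified, infection is the only adverse event proportion listed, and PUSAS and pain ratings do not supply a count. The firmer part is section 8.3, a stated rule that can remove from safety proportions the subjects whose harm ended their participation.

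The size depends on how many subjects leave with an event and no valid final measurement, which the documents do not give. On the plan's own allowance for incomplete data, split evenly, the excluded subjects could account for anything from 0 to 15.0 percentage points of the treated proportion in an arm. The primary comparison and the sample size are unaffected. A descriptive table is feasible; a powered safety comparison is not, unless the difference is large.

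**What to change.** 1. Amend 8.3 so that safety summaries use all randomised subjects who had a study dressing applied, including those later replaced. Keep the evaluable rule out of safety.
2. Add to 8.4, by dressing and descriptively, the number and proportion of subjects with:
   - (a) new or worsened reaction or irritation since the initial visit, from the AE form and the dressing change form, at scheduled and unscheduled changes;
   - (b) infection;
   - (c) any AE, any AE rated possible, probable or definite, any SAE, and worst grade per subject.
3. Give exact two-sided 95% CIs per arm and a 95% CI for the difference.

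Counting from the initial visit separates pre-existing irritation from new irritation. Counting subjects at their worst grade avoids double counting, since 7.6 opens a new form when severity changes.

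**Cost.** Wording in 8.3, 8.4 and the SAP, plus re-tabulation of information the protocol already requires. There are no new visits or procedures and no change in sample size. The intervals will be wide. The format of the irritation item is not shown in the documents; if it records presence only, worsening cannot be derived from it and (a) would be limited to new irritation plus what the AE form records.

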5. STUDY POPULATION

5.1. Inclusion Criteria

A subject will be eligible to participate in the study if he or she satisfies *ALL* of the inclusion criteria below:

- Male or female, ≥ 18 years.
- Subject is able and willing to comply with requirements of this trial protocol.
- Subjects must be able to communicate effectively with study personnel.
- Subject has lower extremity venous ulcer wound, as determined by the site PI.

- Subject has adequate lower extremity arterial circulation as determined by the site PI at the time of enrollment
- Size of subject's wound is between 1cm² and 100cm².
- Duration of subject's wound is < 52 weeks.

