6.2 Day 1 – Initial Visit

6.2.1 Demographics, Comorbidities, and Medication

Demographic information, subject co-morbidities, and a current medication list will be collected in order to understand if these variables affect the endpoints of wound size, periwound skin condition, and subject perception of pain during dressing changes. Information will be recorded on the CRFs.

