6.2.2 Wound photograph and wound size measurement

During the initial visit, a member of the study staff will take photographs of the wound using a specialized wound camera with image analysis software (Insight® by eKare Inc.) and determine area and volume of the wound. The study staff will make every effort to obstruct identifiers such as tattoos/birth marks/scars in the wound images. In the event the camera or software malfunctions, manual measurement with a ruler will occur. Information will be recorded on the CRF.

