8 STATISTICAL CONSIDERATIONS

8.1 Sample Size Determination

A previous pilot study was conducted using a within-subjects design, applying both of the dressings described herein to two different wounds on the same subject, measuring wound reduction and other variables. In that study, the MPS dressing that was used led to a 40% reduction in wound size, whereas the CMS dressing led to a 33% reduction.¹¹ The data was used to determine the appropriate sample size for this study.

A power analysis using G*Power 3.1 for an independent samples t-test indicated that with the above reduction in wound sizes and a 10% standard deviation for each treatment, 68 subjects would be necessary to attain 80% power at a two-tailed alpha of 0.05, assuming a 1:1 assignment to the two dressing groups. A target of 80 subjects will be used in order to account for subjects' lost-to-follow-up and other scenarios that result in incomplete data.

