8.2 Randomization

Local randomization will take place such that each site can randomize subjects into either group without the need for central coordination. Separate randomization lists will be generated for each site in blocks of four, in order to reduce the possibility of an imbalance in group assignment. Randomization lists will be provided in a forthcoming Statistical Analysis Plan (SAP) to be completed prior to study initiation.

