8.3 Populations for Analyses

An evaluable population will be used for all analyses, with evaluable defined as any subject with valid initial visit and final visit wound size measurements.

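### Randomisation is stratified by site and an initial wound size is required for evaluability, but no supplied section puts either in the primary comparison; name both as covariates before the interim

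*Combined protocol and SAP*

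**What the plan says.** - **Primary comparison.** Section 8.4: "The key assessment for differences in dressing performance will be based on the comparison of mean reduction in wound size for each dressing type". It names no covariate, stratum or model, and continues: "The specific details of the statistical testing will be provided in a forthcoming SAP". Section 8.2 says that this SAP is to be finished before the study starts. It is not among the documents.
- **Stratification.** Section 8.2: "Separate randomization lists will be generated for each site in blocks of four".
- **Baseline size.** Section 8.3 analyses only evaluable subjects, with "evaluable defined as any subject with valid initial visit and final visit wound size measurements". At the initial visit, staff use a wound camera to "determine area and volume of the wound" (6.2.2). A ruler is the fallback if the camera or software fails.
- **Spread of baseline size.** Section 5.1: "Size of subject's wound is between 1cm² and 100cm²".
- **Other variables.** Demographics, comorbidities and medication "will be collected in order to understand if these variables affect the endpoints of wound size", among other endpoints (6.2.1). Site and initial wound size are not on that list, and no model is attached to it.
- **Named tests.** Section 8.1 reports "A power analysis using G*Power 3.1 for an independent samples t-test". Section 8.5 describes one-sided group-sequential t-tests.
- **Scale.** Sections 2.1 and 8.1 work in percentage reduction. The synopsis, section 3 and section 8.4 speak only of change or reduction in wound size.

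**The concern.** Stratified randomisation balances the arms within each site, so site differences contribute little to the true variance of the dressing difference. An unadjusted t-test nevertheless leaves between-site variance in its error term. Its standard error is then too large, its type I error falls below 5%, and its interval is wider than necessary. Omitting a prognostic baseline does not make the test conservative; it only gives up precision that data already in hand could supply.

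Timing also matters. The trial is open-label and plans an interim test for efficacy and/or futility (8.5). A covariate set chosen after that look is open to question; one fixed before it is not.

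**Working it through.** **1. Reproduce the plan's figure.** Inputs from 8.1: 40% against 33% reduction (difference 7), SD 10, two-sided alpha 0.05, 1:1. Then d = 7/10 = 0.70, with noncentrality d × √(n/2) and 2n − 2 degrees of freedom.

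- n = 33 per arm: power 79.97%.
- n = 34 per arm: 0.70 × √17 = 2.886 on 66 df, power 81.2%.

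So 34 per arm, 68 in total, reproduces. The target of 80 implies 1 − 68/80 = 15% loss. The plan is sized on an unadjusted t-test.

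**2. Analytic effect of adjustment.** If the covariates explain a share R² of outcome variance, noncentrality becomes 2.886/√(1 − R²), with one df lost for baseline and (sites − 1) for site. R² is not in the documents and is assumed. For 2 to 10 sites:

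| R² | Power at 68 | Total N for 80% |
|---|---|---|
| 0 | 81% | 68 |
| 0.10 | 85% | 60–62 |
| 0.20 | 89% | 54 |
| 0.30 | 92% | 48 |

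This ignores chance imbalance in the covariates, so it slightly understates the cost when R² is 0.

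**3. Simulation at 68.** Permuted blocks of four within site, total SD 10, normal outcomes, difference 7, two-sided 0.05, 10,000 trials per setting. Site count (5), site sizes (14/14/14/13/13 or 24/17/14/8/5), site share of variance and baseline correlation are all assumed. The variance ratio is the squared ratio of CI widths, t-test over ANCOVA; above 1 favours ANCOVA.

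| Site share, correlation | t-test power | ANCOVA power | Variance ratio |
|---|---|---|---|
| 0, 0 | 81.1–81.4% | 80.5–80.7% | 0.976 |
| 5%, 0 | 81.7–82.3% | 82.1–82.8% | 1.018–1.019 |
| 5%, 0.3 | 82.0–82.1% | 85.4–85.6% | 1.118–1.119 |
| 10%, 0.3 | 82.1–82.8% | 86.6–87.1% | 1.16–1.17 |
| 20%, 0.4 | 84.2–84.4% | 93.1–93.2% | 1.39–1.40 |

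Mean 95% CI widths, t-test against ANCOVA: 9.6–9.7 against 9.8 points (first row), 9.5–9.6 against 8.8–8.9 (10%, 0.3), and 9.4–9.5 against 8.0 (last row).

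Type I error of the t-test: 4.2–4.8% at 5% site share, 4.0–4.5% at 10% and 3.2–3.7% at 20%. With site in the model it is 4.6–5.4%.

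With five sites the ANCOVA has 68 − 7 = 61 error df (treatment, baseline and five site terms), against 66. With 3, 5 or 8 sites and no prognostic value, the loss is about 0.5 to 1 point.

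**4. At the interim, n = 46.** Single look, two-sided 0.05, no spending function, neither term prognostic, assumed site sizes: 63.7% against 62.3% with 5 sites (loss 1.4 points) and 64.0% against 62.3% with 8 (loss 1.7). Variance ratios for (0, 0), (5%, 0), (10%, 0.3) and (20%, 0.4) are 0.968, 1.001, 1.139 and 1.332.

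**5. Departure from normality.** If some wounds heal and score 100 (5% or 10%, equal in both arms), the reduction in variance from adjustment shrinks. The variance ratio exceeds 1 by 1–9% if healing is unrelated to baseline area, and by 13–21% if smaller wounds heal more often.

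**The case against.** **The SAP may already do this.** True, and it limits the point. A reader might infer that the primary analysis will be an unadjusted t-test. The documents do not support that: sections 8.1 and 8.5 name a t-test for sizing and for the interim, and 8.4 leaves the final test open. What stands is that nothing supplied names the covariates.

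**Nothing is invalid or underpowered.** Also true. A reader might infer inflated type I error, but the error goes the other way. In every normal-outcome setting above, the t-test keeps at least 81% power.

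**The gain is assumed.** Correct. The documents give no site count, site variance or baseline correlation. Percentage reduction is already divided by baseline, so its correlation with baseline area could be small. In the healing check with healing unrelated to baseline, t-test power falls to about 40% (5% healed) or 24% (10% healed). The outcome distribution could therefore matter more than the covariates, and adjustment does not solve that.

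**The cost at the interim is larger than at the end.** A reader might take 1 point as the worst case. It is not: the loss at 46 is about 1.4 to 1.7 points, and the model has not been evaluated under the three-stage design in 8.5.

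**Baseline area is not strictly guaranteed.** Section 8.3 requires wound size, and 6.2.2 allows a ruler with no stated conversion to area. The fix has to close that gap.

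**Log scale and pooling are choices.** Neither has a source in the documents. In an assumed eight-site layout (16/13/11/9/7/5/4/3), pooling sites under 8 merges 7 + 5 + 4 + 3 = 19 of 68 subjects (28%), so the model departs from the strata. The power cost was at most about 0.5 point.

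**Conclusion.** The point holds as a gap in pre-specification that bears on efficiency. Site is the randomisation stratum and initial wound size is required of every analysed subject, but no supplied section uses either in the primary comparison. An unadjusted t-test would be valid, conservative if sites differ, and less precise than the data allow.

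The size rests on assumed inputs. At 68 subjects it runs from a loss of under 1 point of power to a gain of about 9 points (84.2–84.4% to 93.1–93.2%), and it may be nil. The power levels assume the plan's SD of 10 and normal outcomes, so they show relative precision only. The documents do not support a stronger conclusion, either that the planned test is wrong or that the trial is too small. The change is worth making because the cost is small and the choice should precede the interim.

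**What to change.** In 8.4 or the SAP, before the interim, state the following.

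- The primary endpoint is percentage reduction in wound area from initial to final visit, the percentage scale used in 2.1 and 8.1. Repeat this in the synopsis and section 3.
- The dressings are compared by ANCOVA with treatment, site and baseline wound area. Log area is suggested because eligibility spans 1 to 100 cm².
- Very small sites are pooled by a rule fixed in advance and based on subject counts only. The rule says whether site categories are set afresh at each look, since a site pooled at 46 may stand alone at the end.
- Ruler measurements are converted to area by a stated rule.
- The adjusted difference is reported with its 95% CI, and the unadjusted t-test is kept as a sensitivity analysis.
- The same covariates are used at the interim.

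Cost: wording and a few lines of SAS, using data already collected. If neither covariate is prognostic, power falls by about 0.5 to 1 point at 68 and about 1.4 to 1.7 points in a single look at 46, under assumed site counts. The figures of 68 and 80 do not change. If the SAP already names such a model, nothing further is needed.
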